## 6 SAMPLE SIZE AND POWER

The risk of finding a difference between groups, even if there really is none, is set at 5% (risk of type I error), while the risk of overlooking a difference between the groups that is actually present is set at 20% (type II error). Individual changes from baseline over time will be calculated and all outcome parameters analyzed using mixed effect analysis. Q-Q plots will be visually examined prior to analysis to ensure that the assumption of normal distribution is not violated. Significance level is set to 0.05.

The minimum relevant difference in VISA-A is set at 15. Based on other studies on pain intensity, we expect a baseline mean of 50. Standard deviation is estimated to be 16 on VISA-A. Power of 80% provides a sample size of 20 participants in each group. We will include 25 patients in each group in case of data loss and no-shows, thereby including a total of 50 patients.

The primary analysis will be blinded and follow the intention-to-treat principle with baseline values as covariates. but we will also perform a per-protocol analysis only including patients performing at least 75% of the training programs and receive the per-protocol injections. No interim analyses will be made.

### **Data processing:**

Entry data is registered in Redcap, where all information from each individual subject is collected.

Each patient is assigned an anonymous unidentifiable project number: AE2019-n.

Project numbers are listed on all CRF and patient diaries.

Folders, CRF and patient diaries are stored blinded only with study numbers in the departments computers. After 12 months follow-up of the last patient, a blinded statistician will make the statistical calculations. After data entry, the patients are divided in two groups: group A and group B by help from independent office employee. The primary investigator will group the patients in the two groups still blinded to the treatment group. All statistics are performed until agreement of the results. Thereafter the blinding is broken.

Analysis of data will take place in consultation with the statistician.

## 7 Adverse events

The adverse effects committee is chaired by JR. All adverse events, defined as any negative or unwanted reactions to the interventions will be recorded. A patient diary will be given to patients at baseline where patients are asked for any adverse events during the first three months. This will capture additional ill effects not reported at the time of their occurrence.

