### Blinding

**Randomization** is performed by an independent office employee not involved in patient care ([name]) using a computer generated randomization schedule (MINIMPY, Maghaei 2010) using permuted block sizes (four to six). The employee is blinded to the block sizes. The allocation of each patient is stored in a computer drive with exclusive access only for the responsible office employee ([name]).

All patients are given consecutive research numbers.

**Patients are blinded** to treatment: The syringe are blinded with tape only showing the patients research number. The content is visually identical and with similar viscosity by mixing intralipid to the placebo injection. There is a risk that blinding will be affected by the known side effects of injection with corticosteroids (flare-up and flushing). Therefore, at the first check-up after the injection, patients are asked which of the two groups they think they have been in.

**Doctors performing the injections are blinded** (JR, CB): The syringe are blinded with tape only showing the patients research number. The content is visually identical and with similar viscosity by mixing intralipid to the placebo injection.

**Data entry investigator are blinded** (JR). All data is transferred from Redcap / CRF to Xcel sheet without knowledge of treatment group allocation. After all data is transferred, the patients are divided into two groups “A” and “B” but still blinded to actual treatment groups, by information from the independent office employe.

**Statistician is blinded** (PSM): After data entry and the patients are divided in two groups: group A and group B still blinded to the actual treatment group, all statistics are performed until agreement of the results. Thereafter the blinding is broken.

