### **Description of load reduction**

For the first 3 months, the patient must refrain from jumping and running activities (impact training). They are allowed to do non-impact training such as cycling, swimming, rowing and strength training. Shoes that do not press into the back of the heel are recommended. After 3 months, they must slowly return to their previous sports activity with jumping and running, without provoking further pain or morning stiffness.

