#### **4.3 Interim analysis and early stopping rules**

Anecdotally, an increased risk of tendon rupture have been reported. To account for this, we have introduced an early stopping rule if the rate of Achilles tendon ruptures exceeds 2 ruptures.

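### The SAP's adverse event definition makes a causal judgement a condition of recording, so the arms cannot be compared on all events

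*SAP*

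**What the plan says.** Section 7 (Adverse events) gives the SAP's only definition: "All adverse events, defined as any negative or unwanted reactions to the interventions will be recorded". It refers to no other definition, in the protocol or elsewhere.

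The same section adds a second route: "A patient diary will be given to patients at baseline where patients are asked for any adverse events during the first three months". Its purpose is given as "This will capture additional ill effects not reported at the time of their occurrence". The SPIRIT table in section 4.4 likewise marks the diary at months 1, 2 and 3 only. Trial Design runs follow-up to 12 months.

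Three other places bear on the point:

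- Description of load reduction keeps patients off running and jumping for the first three months. Then: "After 3 months, they must slowly return to their previous sports activity with jumping and running".
- Section 4.3 names a specific safety worry, "Anecdotally, an increased risk of tendon rupture have been reported", and responds to it: "we have introduced an early stopping rule if the rate of Achilles tendon ruptures exceeds 2 ruptures".
- Blinding describes masked syringes for patients and injecting doctors ("The syringe are blinded with tape only showing the patients research number"). It concedes that flare-up and flushing after corticosteroid may give the allocation away.

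Section 4.2 lists analyses for the primary and secondary outcomes. It does not mention a tabulation of adverse events by arm.

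**The concern.** Randomisation allows harm to be judged by comparing arms, without deciding patient by patient what caused each event. That works only if events are recorded before anyone decides on cause. Here the order is reversed: the word *reactions* places the causal judgement at the point of entry. The word *all* does not repair this, because it covers only events that already meet the definition.

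The events most exposed are those with a ready alternative explanation. An infection can be put down to chance. A tendon injury during the return to running can be put down to the sport. These are also the events where a single-patient judgement is least reliable and a comparison of arms most useful. An event that is never recorded may not be recoverable when the trial is analysed.

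**Working it through.** The plan gives no figure on this point to reproduce. Its one computed number, the sample size, plays no part. The check is a reading of the text, followed by some algebra on what the wording does to a comparison.

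**Step 1. Which routes could capture an event that nobody attributes to treatment?**

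| Route (SAP location) | Causal condition? | Period |
|---|---|---|
| Adverse event record (section 7) | Yes, through the definition | Not limited |
| Patient diary (section 7; Table 1) | Same defined term, no broader one given | Months 1 to 3 |
| VISA-A, morning pain, pain after activity (Table 1) | No | To month 12 |
| Ultrasound of the tendon (section 5; Table 1) | No | Months 1, 2, 3, 6, 9, 12 |
| Rupture count for the stopping rule (section 4.3) | No | Not limited |

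Worsening pain is thus measured whatever its cause. A visible tendon change has scheduled chances of being seen. Infections and other non-tendon events have only the first two routes. A tendon injury blamed on sport has no assured place in the adverse event record, even if a scan shows it.

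**Step 2. Timing.** The diary covers 3 of 12 months, leaving 12 − 3 = 9 months without it. The return to running and jumping begins as the diary ends, so through the whole period of renewed impact loading the section 7 definition governs adverse event recording without the diary.

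**Step 3. Effect on the comparison.** Let p1 and p0 be the true event risks on steroid and placebo, and f1 and f0 the shares left unrecorded because they were put down to another cause.

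- Recorded risks are (1 − f1)p1 and (1 − f0)p0.
- If f1 = f0 = f, as blinding would favour, the recorded difference is (1 − f)(p1 − p0). It shrinks by the factor (1 − f).
- The recorded ratio is then (1 − f)p1 / [(1 − f)p0] = p1/p0, unchanged in expectation.
- The expected recorded count per arm of 25 falls from 25p to 25(1 − f)p, so the ratio is estimated less precisely.
- If f1 and f0 differ, the recorded ratio is (p1/p0) × (1 − f1)/(1 − f0). Reactions that reveal the steroid could make staff or patients readier to attribute events to it (f1 below f0, ratio inflated). The opposite tendency would deflate it.

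The documents give none of p1, p0, f1 or f0, so no numerical size is claimed.

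**The case against.** **The stopping rule.** A reader might infer that a rupture blamed on sport would drop out of the count that stops the trial, and calculate how far that lowers the chance of stopping. The documents do not support this. Section 4.3 counts Achilles ruptures without an attribution condition and does not refer to the section 7 definition. Any such probability would also need rupture risks and an omission rate that the SAP does not give. What remains is that the SAP names no separate route by which ruptures are reported, so a clarifying cross-reference is reasonable.

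**Bias towards no difference.** This is also tempting as a general statement, and too strong. With patients and injecting doctors blinded, similar loss in both arms is the natural expectation. That shrinks the absolute difference and costs precision, but it does not move the expected ratio. Unequal loss requires allocation to be revealed, which the SAP itself treats as possible.

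**Breadth of the wording.** The interventions include training and load reduction as well as the injection, and the gradual return to sport is part of the load programme. A tendon injury during that return can fairly be read as inside the definition. The rest of the definition is broad, and patients may report more in the diary than it strictly asks. This stands as a possible reading, but it leaves staff to choose between readings before recording, and it does nothing for events unrelated to tendon loading.

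**The protocol.** Version 4 is not shown and may hold a fuller definition. The SAP nevertheless states its own and does not defer to another. If the two differ, they need to be reconciled.

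**Conclusion.** The point holds as a defect in a stated definition. Section 7 makes attribution a condition of recording, the diary does not widen it and ends at three months, and no all-event comparison by arm is planned. Non-tendon events such as infection are the most clearly exposed. Tendon injuries blamed on sport after month 3 are exposed on a strict reading. Worsening pain is not materially affected.

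The expected consequence is lost events and an absolute risk difference reduced by the factor (1 − f), in a trial with only 25 patients per arm. This assumes that blinding holds and that the same share is lost in each arm. Distortion of the ratio follows only if that share differs, for instance after unblinding by flare-up or flushing. The efficacy analysis is not affected.

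**What to change.** In section 7:

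1. Define an adverse event as any untoward medical occurrence after randomisation or first injection (choose one and state it), whether or not thought related to the injection, the exercises or the load reduction.
2. Record relatedness as a separate field, judged blind to allocation.
3. Tabulate all events by arm, with related events as a subset.

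In section 4.3, at most add a cross-reference saying that the section 7 definition does not restrict the rupture count. The rule itself need not change for this point.

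Section 4.4 says recruitment had begun when the SAP was signed, so the SAP should also state from what date the new definition applied and whether earlier patients were asked about events retrospectively.

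The cost is SAP and CRF wording, one extra CRF field, and a longer list of minor unrelated events. Treatment and the efficacy analysis are untouched.

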### Description of training with CE approved training app: Injurymap.

The strength training will consist of a gently progressive training program with daily training. The training program starts with gentle exercises without dorsal flexion and is slowly progressed after feedback from the patient. If the patient register pain of 5 or above on a 0-10 scale, the program will choose a lighter exercise and not until 2 weeks later offer the same exercise again. The program consists of both movement exercises, stretching exercises, balance exercises and strength exercises similar to the exercise program we have used and found effective in a previous study (Wetke 2015)

For bilateral symptoms, both sides must be trained, but only one side is included in the evaluation of outcome parameters.

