## **5 OUTCOME MEASURES**

### **Primary outcome measures:**

**The primary endpoint:** VISA-A (total and pain subscales) at 6 months. Collected by blinded evaluator via "Redcap".

All patients are thoroughly instructed in visa-A score, on all visits, as it can be difficult to understand. However, it is important that they fill out the score at home directly in the assessment-app: "Redcap" without interference of any involved investigators. Intention to treat analysis is performed by using mixed effect analysis.

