### **Secondary outcome measures**

Lickert scale at 1, 2, 3, 6, 9 and 12 months: 11 point box scale from -5 to +5, where 0 is the status at entry, +5 is cured, and -5 is much worse.

VISA-A scores (total and pain subscales) at 1, 2, 3, 9 and 12 months.

Thickness of the Achilles tendon measured by ultrasound scan, cross-sectionel image on the thickest of the tendon at 1, 2, 3, 6, 9 and 12 months. The thickness of the "healthy" tendon is also measured for comparison.

Ultrasound Scanning Doppler Activity assessed with Color Doppler at 1, 2, 3, 6, 9 and 12 months.

After 6, 9 and 12 months, it is also assessed how many percentage of previous activity level (from before the injury) they have recovered. The patient himself states this as a percentage.

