#### **4.4 Timing of analyses**

When this statistical analysis plan was signed, recruitment to the trial had started, but analysis had not been initiated.

Statistical Analysis Plan  
Exercise/Injections in Achilles entesopathy

	Enrolment	Allocation	Month 1	Month 2	Month 3	Month 6	Month 9	Month 12
TIMEPOINT**	June 2021 – end June 2023	June 2021 – end June 2023					March 2022 end 2024	June 2022 end 2024
ENROLMENT:								
Eligibility screen	X	X						
Informed consent		X						
Allocation		X						
INTERVENTIONS:								
Intervention group			◆	◆	◆	◆		
Control group			◆	◆	◆	◆		
ASSESSMENTS:								
Diagnosis		X						
VISA-A		X	X	X	X	X	X	X
Morning pain [VAS]		X	X	X	X	X	X	X
Pain after activity [VAS]		X	X	X	X	X	X	X
Return to usual sports participation						X	X	X
Satisfaction with result of treatment			X	X	X	X	X	X
Patient diary for reporting compliance and adverse events			◆	◆	◆			
Ultrasound examinations		X	X	X	X	X	X	X
Demographics		X						

Table 1: SPIRIT figure. Schedule of enrolment, interventions and assessments

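### The only adverse-event question to patients that the SAP describes, the diary, stops at month 3; none is described for months 3 to 12, when running and jumping resume

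*SAP*

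**What the plan says.** SAP section 7 (Adverse events) commits to recording all adverse events, defined as unwanted reactions to the interventions, and gives no end date. It then describes a diary, handed out at baseline, in which "patients are asked for any adverse events during the first three months". It also gives the reason for the diary: "This will capture additional ill effects not reported at the time of their occurrence".

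Table 1 (section 4.4) carries this into the schedule. The row "Patient diary for reporting compliance and adverse events" has three marks, at months 1, 2 and 3. No other row is an adverse-event item. The intervention rows for both arms are marked at months 1, 2, 3 and 6.

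Three other statements bear on the window:

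- Load reduction: impact training is barred for three months. "After 3 months, they must slowly return to their previous sports activity with jumping and running".
- Section 4.3, on rupture: "we have introduced an early stopping rule if the rate of Achilles tendon ruptures exceeds 2 ruptures". It gives neither a time limit nor a method of finding ruptures.
- Follow-up runs to month 12. The outcome sections and Table 1 include a 9-month visit, which the Trial Design paragraph leaves out.

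**The concern.** By its own account the diary exists because some ill effects go unreported unless patients are asked. The SAP describes no such back-up after month 3, yet that is when patients return to running and jumping, with the rupture rule still open.

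Two things are at stake, both about the safety report. First, the rule acts on a count above 2, so at such low numbers one unreported event could decide whether it is met. Second, benefit is judged at 6 months for the primary endpoint and to 12 months for the secondary ones, while harm is actively asked about only to month 3. A reader of the report would be weighing the two over different periods.

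**Working it through.** The SAP states no figure on this point to reproduce, and it gives no risk of rupture or of any adverse event. The number of missed events therefore cannot be computed. What can be checked is the window, what the later visits would pick up, and how many patients a change could still reach.

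**1. The window.** Follow-up is 12 months (Trial Design, Table 1) and the diary covers 3 (section 7, Table 1).

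- Months without a described question: (12 − 3)/12 = 9/12 = 75%.
- Visits without one: months 6, 9 and 12, so 3 of the 6 in Table 1. If there is no 9-month visit, months 6 and 12, so 2 of 5.

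**2. What the later visits would show.** From Secondary outcome measures and Table 1, months 6, 9 and 12 include VISA-A, morning pain and pain after activity on a VAS, the Likert rating, the share of previous activity regained, and ultrasound ("cross-sectionel image on the thickest of the tendon at 1, 2, 3, 6, 9 and 12 months").

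| Event in months 3 to 12 | Route in the SAP | What is left |
|---|---|---|
| Pain or worsening present at a visit | Pain VAS, VISA-A, Likert | Scored, though not logged as an adverse event |
| Rupture, patient attends | Ultrasound | Probably seen |
| Event in a patient who misses the scan | Own report; perhaps a poor score | Not asked about |
| Flare that settles between visits | Own report | Not reliably captured |
| Event other than pain | Own report, unless visible on a scan | Not reliably captured |

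The first two rows are largely covered. The last three are the gap.

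**3. Reach of a change.** Assumptions: even recruitment of 50 patients from 1 June 2021 to 30 June 2023 (760 days, the window in Table 1), no withdrawals, and a change made on one of the SAP's two dates, 29 September 2022 (version page) or 27 November 2022 (page header). A patient is past month m if enrolled at least m months before the change, so the expected number is 50 × (days from 1 June 2021 to the change date minus m months)/760.

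| Past month | Change on 29 Sept 2022 | Change on 27 Nov 2022 |
|---|---|---|
| 6 | 50 × 301/760 = 19.8 | 50 × 360/760 = 23.7 |
| 9 | 50 × 211/760 = 13.9 | 50 × 271/760 = 17.8 |
| 12 | 50 × 120/760 = 7.9 | 50 × 179/760 = 11.8 |

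Patients who could still be asked at least once: 50 − 7.9 = 42.1 down to 50 − 11.8 = 38.2, or about 38 to 42 of 50 (76% to 84%).

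**The case against.** The strongest reply has four parts.

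*The window has a reason.* The randomised difference is the injection, given at 0, 1 and 2 months at most. The diary covers every injection and at least a month after the last. The first three months are not unloaded either, since patients follow a "gently progressive training program with daily training". This stands as a rationale for the diary, but it does not explain why nothing follows it.

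*Late events are not ignored.* A reader might infer that recording stops at month 3, or that a pain flare after return to running would surface only if the patient volunteered it. The documents support neither. The commitment to record has no end date, and pain and worsening are scored on several scales at each later visit. Likewise, nothing shows that ruptures would go undetected: a scan at 6, 9 or 12 months would probably reveal one in a patient who attends. This part stands, and it limits the point to the last three rows of the first table.

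*Patients who miss a scan may miss the form too.* That is partly so. But patients complete VISA-A away from the clinic ("it is important that they fill out the score at home directly in the assessment-app"), so a question placed there can reach some who do not come in.

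*The protocol or CRF may already ask.* The protocol is not at hand, and section 7 treats the diary's yield as additional to other reporting, so this is possible. It does not remove the point, because the SAP itself states a collection window and a full assessment schedule, and both end adverse-event questions at month 3. It does reduce what needs changing.

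**Conclusion.** The point holds as a minor one. The SAP describes no adverse-event question to patients for months 3 to 12, which is 75% of follow-up. That percentage is a share of the calendar, not of missed events. The gap is in asking, not in all recording: flares that resolve between visits, events other than pain, and events in patients who miss a scan.

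A reader might also infer bias between the arms or harm to the main result. Neither is shown. The schedule is the same in both blinded arms, and the primary estimate, power and type I error are untouched.

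The conclusion rests on the SAP alone and on reading the Table 1 marks by column position in extracted text; section 7 independently confirms the three-month window. The reach figures rest on even recruitment and no withdrawals.

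**What to change.** Add one standard adverse-event question, naming tendon rupture and worded as *since you were last asked*, to the existing 6-, 9- and 12-month REDCap forms, so that the first answer reaches back to month 3. If there is no 9-month form, use months 6 and 12. Give the question its own row in Table 1, and state that events will be tabulated by arm, separately for months 0–3 and 3–12. If the protocol or CRF already asks at these visits, only the row and the tabulation need adding.

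The cost is one question on up to three existing forms, one table row and one sentence. There would be slightly more events to code, and the recall period would be three months or longer, which is weaker than a diary. Recruitment had begun when the SAP was signed, so some patients will have passed a visit without being asked; the report should give that number for each visit.
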